# 3.3.6. TN/U Expansion Cohort

Patients in the Expansion stage of the TN/U Expansion Cohort will receive the RP2DS determined in the TN/U Dose Evaluation Cohort. For the TN/U Expansion stage, patients may be enrolled simultaneously without an observation time between patients. The CTSC may alter the dosing scheme including, but not limited to, exploring a dose schedule of weekly or up to Q4W, if supported by emerging PK and clinical safety and efficacy data. Based on emerging clinical data, including efficacy data, the TN/U Expansion Cohort may be increased beyond 30 patients as determined by the CTSC.

Based on a Type B End of Phase 1 meeting with the FDA in May 2019, the TN/U Expansion Cohort was expanded in Amendment 5 to include untreated intermediate to very high-risk MDS patients, as assessed by IPSS-R, to include at least 91 patients as a single-arm trial for a potential BLA in higher-risk untreated MDS. These 91 patients are inclusive of MDS patients already treated in the TN/U Dose Evaluation and Expansion Cohorts. In a Type A meeting with the FDA in November 2019, it was agreed that the primary endpoint for potential approval can be CR rate with duration of CR.

An efficacy evaluation will be made after 36 evaluable MDS patients have undergone the first response assessment. If the CR rate for magrolimab and azacitidine is at least 35.5%, then an additional 56 patients will be treated in expansion at a magrolimab dosing regimen of Q2W. Enrollment does not need to be paused during the 36-patient evaluation prior to the additional 56-patient expansion. The 56-patient expansion would bring the total number of MDS patients in the TN/U Expansion Cohort to n = 92. The overall MDS expansion to 92 patients will be considered the MDS Registrational Cohort.

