#### 10. MEASUREMENT OF EFFECT

Assessment of response will be conducted by the Investigator using the criteria in Appendix B, which are based primarily on the 2017 ELN recommendations for AML (Döhner 2017) and the 2003 IWG criteria (Cheson 2003) for AML patients. Response classifications include: complete remission (CR) rate, morphologic CR, complete remission without minimal residual disease (CRMRD-), cytogenetic complete remission (cCR), molecular complete remission (mCR), complete remission with incomplete hematologic recovery (CRi), complete remission with partial hematologic recovery (CRh), marrow complete remission (CR), morphologic leukemia-free state (MLFS), PR, and stable disease (SD).

In addition, hematologic improvement (HI) will be assessed by 2006 IWG criteria (Cheson 2006) to compare with disease response assessed by 2017 ELN criteria (Döhner 2017) and 2003 IWG criteria (Cheson 2003).

Response will be assessed in MDS patients using the criteria in Appendix B Table 14-4, which are based on the 2006 IWG criteria (Cheson 2006) with the added caveat that the impact of anemia must be deemed disease-related and not due to study treatment.

Response assessments will be performed at the time points specified in the Schedule of Assessments in Section 7.1 and as described in Section 7.9.

The following summary measures for endpoints will be evaluated:

**Objective Response Rate for Patients with AML**: The ORR is the proportion of patients who reach CR (including morphologic CR, CRMRD-, cCR, and mCR), CRi, CRh, PR, or MLFS while on study.

**CR Rate for Patients with AML**: The CR rate is the proportion of patients who achieved CR, as defined by the Investigator based on ELN AML recommendations (Döhner 2017; Appendix B).

**CR Rate for Patients with MDS**: The CR rate is the proportion of MDS patients who reach morphologic CR while on study per IWG 2006 criteria (Cheson 2006).

**Duration of Complete Remission (DCR) for AML**: The DCR is measured from the time measurement criteria are first met for CR (including morphologic CR,  $CR_{MRD}$ -, cCR, and mCR) until the first date that recurrent disease or death with evidence of no disease recurrence is objectively documented. Those who are not observed to have recurrent disease or die with evidence of no recurrence during the trial active period will be censored at their last response assessment date with evidence of no progression/recurrence.

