**Duration of Response (DOR) for Patients with AML**: The duration of response is measured from the time measurement criteria are met for CR (including morphologic CR, CRMRD-, cCR, and mCR), CRi, CRh, PR, marrow CR, or MLFS, whichever is first recorded, until the first date that recurrent or progressive disease, or death with evidence of no disease progression is objectively documented. Those who are not observed to have recurrent or progressive disease or die with evidence of no disease progression during the trial active period will be censored at their last response assessment date with evidence of no progression/recurrence.

**Duration of CR for Patients with MDS**: The duration of CR for MDS patients is measured from the time measurement criteria are first met for CR until the first date that recurrent disease or death with evidence of no disease recurrence is objectively documented. Patients who are not observed to have recurrent disease or die with

evidence of no recurrence during the trial active period will be censored at their last response assessment date with evidence of no progression/recurrence.

Duration of Response for Patients with MDS: The DOR for MDS patients is measured from the time measurement criteria are first met for objective response (including CR, PR, marrow CR, and HI) as assessed by IWG MDS criteria (Cheson 2006) until the first date that recurrent disease or death with evidence of no disease recurrence is objectively documented. Those who are not observed to have recurrent disease or die with evidence of no recurrence during the trial active period will be censored at their last response assessment date with evidence of no progression/recurrence.

**Overall Survival (OS)**: The length of OS is measured from the date of study treatment initiation until the date of death from any cause. Those who are not observed to die during the trial active period will be censored at their last known alive date from survival follow-up.

**Progression-free Survival (PFS)**: The length of PFS is defined as the time from the date of study treatment initiation until the date of documented disease progression or relapse or death from any cause, whichever occurs first (Cheson 2003). Those who are not observed to have one of these events during the time the overall trial remains active will be censored at their last known progression-free follow-up date.

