**Event-free Survival (EFS)**: For AML, the length of EFS is defined as the time from the date of study treatment initiation until the date of documented disease progression, death from any cause, or treatment failure (defined as failure to achieve CR/CRi by Cycle 5 Day 1), whichever occurs first (Cheson 2003). For MDS, EFS is defined as the time from the date of study treatment initiation to transformation to AML or death from any cause, whichever occurs first. Those who are not observed to have one of these events during the time the overall trial remains active will be censored at their last known progression-free follow-up date.

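### Duration of CR and of response can censor responders who die with relapse status unknown; AML EFS omits relapse, and the MDS EFS censoring date does not match its events

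*Protocol*

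**What the plan says.** All the definitions are in Protocol Section 10.

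- **DCR (AML and MDS) and DOR (MDS)** run "until the first date that recurrent disease or death with evidence of no disease recurrence is objectively documented".
- **DOR (AML)** runs "until the first date that recurrent or progressive disease, or death with evidence of no disease progression is objectively documented".
- **Censoring** uses the complement of those events. For AML DCR and MDS DOR: "Those who are not observed to have recurrent disease or die with evidence of no recurrence during the trial active period will be censored". The other two are worded to the same effect. The censoring date in all four is "at their last response assessment date with evidence of no progression/recurrence".
- **PFS** runs "until the date of documented disease progression or relapse or death from any cause, whichever occurs first". OS also counts death from any cause.
- **EFS (AML)** runs "until the date of documented disease progression, death from any cause, or treatment failure". Treatment failure there means no CR/CRi by Cycle 5 Day 1.
- **EFS (MDS)** has two events, transformation to AML and death from any cause. Patients without an event "will be censored at their last known progression-free follow-up date".

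On the role of duration of CR, Section 3.3.6 records that "it was agreed that the primary endpoint for potential approval can be CR rate with duration of CR". Section 2.2.2 lists it as a secondary endpoint. Section 11.8.1.1 formally tests only the CR rate.

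**The concern.** In the four duration endpoints a death is an event only under a condition on disease status. A responder whose relapse was suspected but not documented, or whose status was unknown, meets neither branch of the event clause and falls into the censoring clause. Such a patient is probably close to relapse, so the censoring is informative and leaves out events that end remission.

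Duration of CR supports the CR rate in the potential approval. At the planned 92 patients and 36.5% CR rate (Section 11.4), about 34 patients contribute to it (92 × 0.365 = 33.6), so three or four censored deaths are about 10% of the largest possible number of events.

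The two EFS faults matter less, but they also change results. One lets a relapse be a PFS event and not yet an EFS event. The other removes follow-up time for a reason that is not an EFS event.

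**Working it through.** The protocol states no assumed median, power or sample size for DCR, DOR or EFS, so there is no figure to reproduce. The check is of the definitions, with illustrations of direction and size.

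**(a) DCR and DOR.** Responders fall into these classes:

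1. Recurrence documented, then death: the recurrence is the event and nothing is lost.
2. Death with evidence of no recurrence: event.
3. Death without documented recurrence and without evidence of its absence: not an event, censored at the last clean assessment.
4. Alive without recurrence: censored, correctly.

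Class 3 is foreseeable. In the R/R and TN/U cohorts, marrow assessments after Cycle 7 are every 3 cycles (3 × 28 = 84 days; Section 7.3.8). Disease follow-up stops at new anti-cancer therapy (Section 7.6), while survival follow-up continues (Section 7.7).

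*Direction.* Turning a death into a censored observation removes a downward step, so the Kaplan-Meier curve is higher from the date of death onwards. Between the last assessment and the death the patient also leaves the risk set, which offsets a little of this.

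*Size.* Take a constant hazard h with true median ln 2 / h. If a share f of events is censored, the apparent hazard is (1 − f)h and the apparent median is the true median / (1 − f). For an assumed true median of 12 months:

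- f = 10%: 12 / 0.9 = 13.3 months
- f = 20%: 12 / 0.8 = 15.0 months

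A simulation (200,000 patients per scenario) also moved the censoring date back to the last assessment. Its assumptions, none taken from the protocol, were:

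- exponential durations;
- assessments every 2.8 months;
- administrative censoring at 12 to 36 months;
- 20% or 40% of first events being deaths without documented recurrence;
- 25%, 50% or 100% of those deaths lacking evidence of no recurrence, so that about 5% to 40% of events were lost.

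| True median (months) | Reads under the protocol rule |
|---|---|
| 6 | 6.2 to 9.4 |
| 10 | 10.5 to 16.0 |
| 15 | 15.7 to 24.4 |

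All 18 scenarios moved upwards. The formula gives slightly more than the simulation (true median 10, f = 20%: 10 / 0.8 = 12.5 against 12.3) because of the offset noted above.

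**(b) AML EFS.** PFS names progression and relapse separately; EFS names progression only. A patient who has reached CR or CRi by Cycle 5 Day 1 has not failed by that rule. Progression in Table 14-1 is measured against baseline: marrow blasts must rise more than 50% over baseline, with a 15-point minimum increase at lower baselines (read here as below 30%). The marrow thresholds are then:

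- baseline 20%: the larger of 20 × 1.5 = 30 and 20 + 15 = 35, so above 35%
- baseline 30%: 30 × 1.5 = 45, so above 45%
- baseline 40%: 40 × 1.5 = 60, so above 60%

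A patient with 40% blasts at baseline who reaches CR and relapses at 50% is below the 60% threshold. By the marrow criterion that relapse is a PFS event and not an EFS event. EFS runs on until progression by any criterion, or death.

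**(c) MDS EFS.** Only patients without transformation or death are censored. Someone who progresses within MDS and later transforms or dies still counts as an event at its true date. Someone who progresses and stays event-free is censored back at the last progression-free date. Events stay fixed while later risk sets shrink, so each factor 1 − d/n (d events, n at risk) falls or stays the same and the curve is never higher. In four illustrative scenarios (exponential times, median time to progression 8 to 18 months, higher hazard after progression, administrative censoring at 18 to 54 months), true medians of 20.1, 19.1, 22.6 and 22.3 months read 18.3, 18.4, 18.2 and 21.2.

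**The case against.** **On (a).** The censoring sentences treat a clean assessment as evidence of no recurrence. Read the same way, a responder who dies after a clean last assessment has such evidence and is an event. This is a fair reading and it rescues some deaths. It does not settle deaths with suspected but undocumented relapse, or deaths long after disease follow-up ended. The sponsor may have meant death with no evidence of recurrence, but that is a different condition, and the written one appears in both the event and the censoring clauses.

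Such deaths may also be few. MDS relapse after CR can be documented from counts, hemoglobin or transfusion dependence (Table 14-4), and blood counts are taken on Days 1 and 15 from Cycle 3 (Table 7-2). Response is assessed at end of treatment, a marrow is due at safety follow-up if none was done in the prior 4 weeks, and marrows then continue about every 8 weeks (Sections 7.3.8 and 7.9). All this limits the number without removing the gap.

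**On (b).** Section 6.1 explains disease progression as including relapse after CR/CRi, which would bring relapse into EFS. But that is a rule on continuing treatment, and Section 10 itself lists relapse separately in PFS and treatment failure separately in EFS. A reader might infer that relapses are lost for good, or that Table 14-1 lacks a relapse definition. Neither is supported: most relapses would reach EFS later through progression or death, and the progression entry in Table 14-1 breaks off in the text available here.

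**On (c).** A reader might infer that this rule also lengthens EFS, by removing patients just before their risk rises. It does not, because patients whose later event is observed are kept.

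**Conclusion.** The definitions need correcting in three places, with different effects.

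- **DCR and DOR:** as written, deaths with suspected or unknown relapse can be censored, which biases the duration upwards. The protocol gives no share of such deaths. The 10% and 20% figures are assumptions, not predictions, and the effect is nil if no such death occurs.
- **AML EFS:** the text is inconsistent with PFS and with Section 6.1. A relapse below the baseline-referenced criteria can be a PFS event but not an EFS event until later progression or death.
- **MDS EFS:** the censoring date does not match the events, and the mismatch tends to shorten the estimate.

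It would go too far to say that all these endpoints are overstated, or that all deaths in responders are dropped. Nor is the registrational test affected: duration of CR has no formal test, and its weight comes from being paired with the CR rate for potential approval. The SAP may settle the handling of missing data, but these event definitions are fixed in the protocol.

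**What to change.** In Section 10:

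1. **DCR and DOR, AML and MDS:** end at recurrence (or progression, where it applies) or death from any cause, whichever is first. Censor only patients alive without recurrence or progression, at the last response assessment showing none.
2. **AML EFS:** add relapse after CR/CRi to the events, and reconcile the use of progression in Sections 6.1 and 10. No new row in Table 14-1 is requested.
3. **MDS EFS:** censor at the last date known alive and free of AML.

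Carry the same wording into the SAP. The cost is text and programming; deaths and relapses are already collected. DCR and DOR may come out somewhat shorter, AML EFS may be shorter where a relapse now counts earlier, and MDS EFS may be somewhat longer.

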### 6.4. Patient Completion of the Study

Patients are expected to remain on study treatment until at least completion of Cycle 6. Patients who have not demonstrated disease progression or unacceptable toxicity may continue to receive study treatment beyond 6 cycles.

Patients are considered to have completed the study treatment period when they finish the Safety Follow-up Visit 30 days (± 7 days) after their last dose of study treatment, unless they are experiencing ongoing serious adverse events (SAEs) or treatment-related AEs. For patients being followed for ongoing SAEs or treatment-related AEs, follow-up visits will continue at least Q4W until resolution to baseline or stabilization of these events, unless the patient starts another anti-cancer treatment. Follow-up for ongoing SAEs or treatment-related AEs after the Safety Follow-up Visit will stop if a patient begins another anti-cancer therapy.

After the Safety Follow-up Visit, patients will enter long-term follow-up for disease progression (Section 7.6) and survival follow-up (Section 7.7).

All patients, including those who discontinue study treatment early, will be followed for response until disease progression or initiation of new anti-cancer therapy, whichever happens first, and followed for survival until death or 3 years after the date of enrollment of the last patient, whichever happens first. For patients who come off study treatment to receive a bone marrow transplant, follow-up for disease progression and collection of SOC bone marrow biopsy/aspirate results will continue until documented disease progression occurs. For any patient who dies during this period, the cause of death must be reported to the Sponsor. All patients must also be followed through completion of all study treatment.

Patients are considered to have completed study participation altogether when they are no longer followed for disease progression or survival (refer to Section 8 for additional details about study discontinuation).

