## 7.6. Long-term Follow-up for Disease Progression

Patient will be followed until disease progression or until they begin a new anti-cancer therapy, whichever happens first.

- Correlative studies (at time of disease progression)
- Bone marrow biopsy for response assessment (Section 7.3.8 and Section 7.9)
- Response Assessment (± 14 days), every 8 weeks (Section 7.9)

Following the Safety Follow-up Visit, patients with ongoing SAEs and study drug-related AEs will be followed for safety. If any SAEs or study drug-related AEs are ongoing after the Safety Follow-up Visit, follow-up with the patient will occur at least Q4W until resolution to baseline or stabilization of these events, unless the patient starts another anti-cancer treatment. Follow-up will stop when a patient begins another anti-cancer treatment. For patients who come off study treatment to receive a bone marrow transplant, follow-up for disease progression and collection of SOC bone marrow biopsy/aspirate results will continue until documented disease progression occurs.

The long-term care of the patient will remain the responsibility of his/her primary treating physician.

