## 7.7. Survival Follow-up

All patients who permanently discontinue all study treatment will be contacted during a clinic visit or by telephone to assess survival, and the commencement of new anti-cancer therapy following the last administration of study drug (if not documented previously). Patients will be contacted every 2 months (± 1 month) from the date of the Safety Follow-up Visit, until 3 years from the date that the last patient is enrolled in the study, unless there is full withdrawal of consent. The patient's primary physician or family may be contacted by the Investigator in order to obtain survival information in case the patient cannot be reached. For any patient who dies during this period, the cause of death must be reported to the Sponsor.

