	more advanced MDS FAB subtype than pretreatment
Relapse after CR	At least 1 of the following:
or PR	Return to pretreatment bone marrow blast percentage
	
 
Decrement of ≥ 50% from maximum remission/response levels in granulocytes or platelets
 

	• Reduction in Hgb concentration by ≥ 1.5 g/dL or transfusion dependence d
Cytogenetic	Complete: Disappearance of chromosomal abnormality without appearance of
Response	new ones
	Partial: At least 50% reduction of the chromosomal abnormality
Disease	For patients with:
Progression	• Less than 5% blasts: ≥ 50 increase in blasts to > 5% blasts
	5%-10% blasts: ≥ 50% increase in blasts to > 10% blasts
	10%-20% blasts: ≥ 50% increase in blasts to > 20% blasts
	20%-30% blasts: ≥ 50% increase in blasts to > 30% blasts
	Any of the following:
	At least 50% decrement from maximum remission/response in granulocytes or platelets
	• Reduction in Hgb by ≥ 2 g/dL d
	Transfusion dependence d

Source: Cheson 2006

Abbreviations: CR = complete remission; FAB = myelodysplastic syndrome French-American-British classification; Hgb = hemoglobin; IWG = International Working Group; MDS = myelodysplastic syndrome; PR = partial remission.

- a. Dysplastic changes should consider the normal range of dysplastic changes
- b. Modification to IWG response criteria
- c. Transient cytopenias during repeated chemotherapy courses should not be considered as interrupting durability of response, as long as they recover to the improved counts of the previous course.
- d. Impact of anemia must be deemed disease-related and not due to study treatment.

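### MDS event-free survival counts AML transformation, but its date is not collected after progression or new therapy, and the censoring date belongs to a different endpoint

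*Protocol*

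**What the plan says.** **Event and censoring (Section 10).** "For MDS, EFS is defined as the time from the date of study treatment initiation to transformation to AML or death from any cause". Patients without an event "will be censored at their last known progression-free follow-up date". That censoring sentence closes the EFS paragraph for AML and MDS alike and matches the one used for PFS.

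**End of disease follow-up.** Section 7.6: "Patient will be followed until disease progression or until they begin a new anti-cancer therapy, whichever happens first". Section 6.4 agrees: patients "will be followed for response until disease progression or initiation of new anti-cancer therapy, whichever happens first, and followed for survival until death". Section 8.1 and Table 7-5 set the same stop. Patients who leave treatment for a transplant are followed past it, but again only to documented progression.

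**After that stop (Section 7.7 and Table 7-5).** Patients are "contacted during a clinic visit or by telephone to assess survival, and the commencement of new anti-cancer therapy". Contacts are every 2 months, in Section 7.7 "until 3 years from the date that the last patient is enrolled in the study", and cause of death must be reported. Transformation to AML is not an item.

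**What counts as MDS progression (Table 14-4).** Blasts rising past 5% or 10%, a 50% fall in granulocytes or platelets, transfusion dependence, or "Reduction in Hgb by ≥ 2 g/dL". A footnote requires anemia to be disease-related and not due to study treatment.

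**Adverse event reporting (Section 9.3.1.6).** Non-fatal progression is not routinely an AE or SAE. It is left to the efficacy assessments.

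**The concern.** The endpoint needs transformation to be observed until death or end of study. The protocol stops looking at an earlier milestone that is not an event for this endpoint. Most Table 14-4 criteria describe disease that has worsened but is not yet AML, so the patients who leave disease follow-up are those in whom transformation is the next thing to watch for.

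Two separate problems follow. A transformation after the stop is not seen, so the EFS event moves to the later date of death or, if the patient is still alive, does not appear. And a living patient who has progressed without AML is censored back at the progression-free date because of something that is not an event, which makes the censoring informative.

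The protocol describes higher-risk MDS as carrying a high risk of leukemic progression and treats this cohort as a potential pivotal single-arm study. There is no concurrent arm in which the same error would occur and cancel.

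**Working it through.** **1. The passages side by side.**

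| Question | MDS EFS needs | Protocol provides |
|---|---|---|
| Event | AML or death | AML while disease follow-up lasts; death throughout |
| Disease follow-up ends | At AML, death or study end | At progression or new therapy (6.4, 7.6, Table 7-5) |
| Content of later contacts | Date of transformation | Vital status, new therapy, cause of death (7.7) |
| Censoring date | Last known alive and AML-free | Last known progression-free (Section 10) |

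The protocol states no EFS figure, so there is none to reproduce.

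**2. Assumed inputs (none is in the protocol).** Exponential times. Median 12 months to progression and 36 months to death without progression. A share f = 20% or 40% of progressions is AML at once. For the rest, median m = 4 or 8 months from progression to AML and 10 months to death without AML. Median 5 months from AML to death. Follow-up 36 months. Transformation after a non-AML progression is treated as never seen.

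**3. How many transformations are unrecorded.** Without a follow-up cutoff, the share of patients who transform after a non-AML progression is

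36/(12+36) × (1 − f) × 10/(10+m)

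- f = 20%, m = 4: 0.75 × 0.8 × 10/14 = 43%
- f = 20%, m = 8: 0.75 × 0.8 × 10/18 = 33%
- f = 40%, m = 4: 0.75 × 0.6 × 10/14 = 32%
- f = 40%, m = 8: 0.75 × 0.6 × 10/18 = 25%

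These count transformations later than any 36-month follow-up could record. Applying the cutoff by simulation, the range is 22–39% of patients. Most of them die within follow-up, so the event is late rather than absent. About 3–4% of patients have an unseen transformation and no later EFS event.

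**4. Effect on the Kaplan-Meier median at 36 months (months).**

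| f, m | All transformations seen | Protocol rules | Overstatement | Unseen, but censored at last contact |
|---|---|---|---|---|
| 20%, 4 | 11.7 | 14.8 | 3.1 | 14.9 |
| 20%, 8 | 13.1 | 15.4 | 2.3 | 15.6 |
| 40%, 4 | 11.1 | 13.3 | 2.2 | 13.4 |
| 40%, 8 | 12.1 | 13.7 | 1.6 | 13.8 |

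Simulation error is about 0.1 month. The last column isolates the censoring rule: against censoring at last contact, the protocol's date lowers the recorded median by 0.1–0.2 month. It discards the later event-free time of living patients, while deaths after progression still count. With follow-up of 6–24 months the same comparison gives a lowering of about 1 to 1.6 months.

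**5. Wider assumptions.** A second grid varied the median time to the follow-up stop (8 or 12 months), the share of stops that are AML (15% or 40%), stop to transformation (6, 12 or 24 months) and stop to death (8 or 16 months), with a 40-month median for death before the stop.

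- Mature follow-up (36–60 months): median EFS overstated in all 24 scenarios, by 0.7 to 6.3 months, with 26–80% of transformations missed.
- Early cut (6–24 months): the error in the median runs from −1.5 to +2.8 months.
- One mature scenario gives an OS close to the 18 months that Section 1.5.1 cites for hypomethylating agents (stop 12 months, 15% AML at the stop, 12 to transformation, 8 to death). Recorded median EFS is 16.4 months against 14.0, and 24-month EFS 32.4% against 25.9%.

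**The case against.** **Assessment does not always stop at first progression.** Section 8.1 advises treating on until progression is confirmed at least 4 weeks later or treatment no longer helps. Section 3.2 lets monotherapy responders who progress add azacitidine and continue. On-treatment marrows go on meanwhile. This stands, and the simulations ignore it. If 30% of patients kept their assessments after progression (an assumption), an overstatement of about 1.5–3.1 months would fall to about 1.1–2.1. It reduces the gap without closing it.

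**General wording.** The synopsis and Section 3.1 say patients are observed for disease progression and survival until death or study end. Those sentences do not mention transformation, and the operative sections and Table 7-5 stop disease assessment earlier.

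**Cause of death is reported.** It may show that AML occurred, but not when, and says nothing about living patients.

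**The SAP may deal with it.** Section 11.8 leaves missing data and withdrawals to the SAP, which is not shown. A SAP cannot recover dates that were never collected.

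**Stronger readings a reader might infer.** One is that the censoring rule also inflates EFS, so both faults push upward. The calculation shows the reverse. Another is that later transformations are simply lost. Death is itself an event and survival is followed every 2 months, so most are delayed. A third is that the registrational result is affected. It rests on CR rate with duration of CR, neither of which uses this definition.

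**Conclusion.** The mismatch is in the text and needs no assumption: the event is transformation or death, collection stops at a different and usually earlier point, and the censoring date belongs to PFS. Following the protocol exactly gives a biased MDS EFS.

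Size and direction do rest on assumption. For the rates in step 2, missed transformations overstate the mature median by about 1.6 to 3.1 months, an upper bound for those rates because no assessment after progression is assumed. Other assumed rates give other sizes (step 5). Upward bias is the consistent result only for mature data, which is what the planned final analysis uses (data through study discontinuation). At an early cut the two faults oppose each other and the sign is not fixed.

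EFS is one of many secondary endpoints, with no hypothesis, power or sample size attached. The correction should be made, but nothing in the primary analysis depends on it.

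**What to change.** 1. **Section 7.7 and Table 7-5.** For MDS patients, add transformation to AML (yes/no, date, basis) to the existing 2-monthly survival contact, until death or the end of survival follow-up, regardless of progression or new therapy.
2. **Section 10.** Give MDS EFS its own censoring sentence: the last date known alive and free of AML.

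Make both changes together. Moving the censoring date while transformations remain unseen would increase the overstatement, as the last column of the table in step 4 shows.

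Cost: one eCRF item on a contact that already takes place and one sentence in Section 10, with no new visit, marrow or change to treatment. Survival contacts continue after enrollment closes, so the item can still be added. The small downside is that post-treatment transformation dates will rest on local records.
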